Walking impairments and falls are common in older adults and in people with neurological diseases with devastating consequences on health; including serious injuries, activity limitations, social isolation and mortality [8-11]. While studies have shown that walking is often slow and variable in these populations, gait impairments become more pronounced during DT [12-15] or complex walking conditions [16, 17]. For instance, walking is often less automatic in people with neurological disease as demonstrated by DT-cost on walking velocity up to 30% in these populations [12, 13] compared to only 5-10% in healthy individuals [1]. These findings suggest that movements in people with neurological disease are more under executive than automatic control (i.e. attention is required to “how” the body is moved). Similarly, as we age, walking becomes more affected by divided attention (DT) [18, 19], likely contributing to an increased risk of falling in this population [9, 20]. The ability to efficiently and safely adapt the gait pattern is often impaired in people with neurological disease; such as PD [21], MS [22] and stroke [23]. Walking and turning ability, in particular, are vital aspects of mobility that deteriorate with age and are further impaired in people with neurological diseases. Such deficits have been linked with reduction in automatic control of movement and the need for compensatory cognitive cortical control via the pre-frontal cortex (PFC) [24-26], however the underlying neural mechanisms remain unclear. Establishing robust methodology to examine cortical activity during DT and complex walking conditions may aid in the understanding of mobility deficits and support the development of appropriate interventions for older adults and people with neurological diseases.

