properties of light. During testing, study participant is wearing a tight cap fitted to the head and a controller box attached as a light back-pack (approx. 800 g). The recipient box is connected to the cap with a bundle of cables organized on the back of study participants trunk and neck. fNIRS collecting data from the cortex up to 2-3cm deep, it is well suited to study cortical involvement in cognitive processes. The wireless fNIRS system records (50 Hz) changes in oxygenated hemoglobin (HbO₂) and deoxygenated hemoglobin (HHb) including 8 Source-receiver pairs allowing for 64-data channels. Distance from each sources to detector is 3 cm [39] and data will be collected in line with previous studies [30, 40]. To allow for removal of peripheral interference (i.e., from blood flow changes in the extra-cerebral layers of the head), this system also includes short-separation reference channels spread on the left and one right hemisphere which enable measurement of extra-cerebral blood flow [31, 32].

Test procedure. All testing will be conducted by a healthcare professional or a researcher in the project group with experience of balance and gait assessment, and patients with neurology diseases. The participants will perform different postural tasks and walking tests requiring different level of motor-cognitive performance. The conditions will include;

1. standing quite (reference conditions)
2. walking straight in a self-selected and brisk walking speed
3. continuously turning task, walking turns in a self-selected speed where participants follow a predefined track directed by cones placed on floor

The duration of these test conditions will range between 1 to 6 minutes. All test conditions will be performed as a single-task; participants are instructed to focus only on the postural/motor task, and as a dual-task; with concomitant cognitive tasks, such as the Auditory Stroop test, n-back, Stroop Color and Word Test. Condition order will be randomized, with breaks between tasks if needed.

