Data management and analysis. Gait parameters will be processed using the Mobility Lab™ Software and outcomes will be average and variability metrics (e.g. SD) of temporal and gait parameters for each gait condition. Cortical activity will be processed and analyzed using Aurora fNIRS (NIRSport 2 acquisition) software and programming software's, such as MATLAB (Mathworks, MA, USA). Analysis of fNIRS data includes the following steps: data filtering (i.e. removing high frequency noise), baseline correction (i.e. removing the mean/median of the initial a standing reference trial), reference channel correction (i.e. correcting from artefacts, e.g. caused by breathing, cardiac cycle and vasomotor). The outcomes will be change in oxygenated hemoglobin (HbO₂) from baseline standing to the walking conditions, which is a proxy for cortical activation. HbO₂ will be used as a primary outcome due to its sensitivity to walking and cognitive tasks [41]. For both gait and cortical activity outcomes, we will calculate the potential change between less complex postural tasks (e.g. sitting and standing) and more complex motor tasks (e.g. continuously turning task and obstacle crossing). Dual-task interference will also be calculated as the absolute and relative change (percentage) between single-task and dual-task performance.

Assessment of physical activity behavior (part 2)

Instruments and procedure. After completing part 1, the participants will be equipped with one accelerometer (Actigraph GT3X+) [42] and a GPS (i-gotU GT-600) in order to assess the participants physical activity in the community. Both the accelerometer and GPS sensors are lightweight (about 20 gram each) and will be attached to an elastic belt around the hip. The participants will be asked to wear the devices in their daily life during all woke hours for 7 consecutive days and to fill in the diary of the times the device was worn. After the 7-day measurement period, participants will return the device to the research coordinator using a pre-paid mail service. The participants will also receive instruction on how to attach, wear and remove the device as well as brief written information about this procedure.

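### A percentage dual-task change is not a sound measure for standing-subtracted HbO2: it is undefined at zero and reverses sign when the single-task value is negative

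*Combined protocol and SAP*

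**What the plan says.** The relevant text is in the protocol's part 1 section on data management and analysis.

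- **The HbO2 outcome.** It is the change in oxygenated haemoglobin "from baseline standing to the walking conditions, which is a proxy for cortical activation". The processing steps include "baseline correction (i.e. removing the mean/median of the initial a standing reference trial". HbO2 is named as a primary outcome.
- **The next sentence** covers both outcome types: "For both gait and cortical activity outcomes, we will calculate the potential change between less complex postural tasks" and more complex motor tasks.
- **The sentence after that** says that dual-task interference, too, will be "calculated as the absolute and relative change (percentage) between single-task and dual-task performance". It exempts no outcome and gives no denominator. It has no rule for zero or negative single-task values and ranks neither measure first.

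The test procedure lists "standing quite (reference conditions" as the first condition, and then says: "All test conditions will be performed as a single-task; participants are instructed to focus only on the postural/motor task", and also as a dual-task.

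The only percentage dual-task costs that the protocol cites are in the Background and concern gait, for example "DT-cost on walking velocity up to 30% in these populations".

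**The concern.** A percentage change makes sense when the denominator is positive and its zero means that none of the quantity is present. Walking velocity meets both conditions. Standing-subtracted HbO2 meets neither: its zero is a chosen reference level, and a participant can fall on either side of it.

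The absolute and percentage results for a primary outcome could therefore be reported side by side and point in opposite directions, with no rule for which one counts. Aim 3 compares cortical activity across the five groups. A group with more single-task values near or below zero would have a distorted percentage even if its absolute response were the same as that of another group.

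**Working it through.** **Does the sentence cover HbO2?** It says interference will also be calculated, straight after a sentence on both gait and cortical activity. Aim 3 describes performance with regard to both cortical activity and motor behaviour. HbO2 is therefore included on the natural reading, although this is inferred and not stated.

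**Algebra (no assumed distribution).** Let ST and DT be the standing-subtracted HbO2 scores in the single-task and dual-task conditions. With the usual formula, percentage = 100 × (DT − ST)/ST. The same rise of 0.10 (arbitrary units) gives:

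| ST | DT | DT − ST | Percentage |
|---|---|---|---|
| 0.20 | 0.30 | +0.10 | +50% |
| 0.02 | 0.12 | +0.10 | +500% |
| 0.001 | 0.101 | +0.10 | +10,000% |
| 0 | 0.10 | +0.10 | undefined |
| −0.02 | 0.08 | +0.10 | −500% |
| −0.20 | −0.10 | +0.10 | −50% |

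The percentage also depends on the standing reference. Take the first row and move the reference so that both scores shift by +0.10: the result is 100 × 0.10/0.30 = +33.3%. A shift of −0.15 gives 100 × 0.10/0.05 = +200%. The absolute change is 0.10 each time.

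**Size (inputs assumed).** The plan states no figure to reproduce, and the only input it supplies is 50 participants per subgroup. Let r be the single-task mean divided by its SD. Under normality the share with a negative ST is Φ(−r), where Φ is the standard normal distribution function.

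For group summaries, 20,000 trials of n = 50 were simulated with ST ~ N(r, 1) and DT = ST + 0.3 + N(0, SD 0.5), in units of the single-task SD. The true effect is thus a rise of 0.3 SD.

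| r | 0.25 | 0.5 | 1 | 2 | 3 |
|---|---|---|---|---|---|
| Participants with ST < 0 | 40% | 31% | 16% | 2.3% | 0.1% |
| About how many of 50 | 20 | 15 | 8 | 1 | 0 |
| Trials with negative mean of individual percentages | 46% | 42% | 33% | 12% | 2% |
| Trials with negative median of individual percentages | 26% | 10% | 1% | 0% | 0% |
| Trials with negative percentage from the two group means | 3.9% | 0% | 0% | 0% | 0% |

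The absolute group mean is negative in under 0.1% of trials at every r. Direct calculation agrees: its standard error is 0.5/√50 = 0.071, so a true rise of 0.3 lies more than four standard errors above zero.

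**Sensitivity.** With a larger true rise of 0.5 SD (4,000 replicates), the mean percentage is negative in 45%, 39%, 28%, 10% and 1% of replicates. If ST and DT have equal variance and correlation 0.5, so that the SD of change is 1.0 and the rise is again 0.3, the figures are 63%, 58%, 47%, 19% and 3%. About 1.6% are negative on the absolute scale in that case.

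**Standing as a special case.** The test procedure runs standing as single-task and dual-task. If HbO2 interference were computed there, the single-task value would be zero by construction when it is the reference trial itself. If it came from a separate standing trial, it would scatter around zero and about half of participants would have a reversed sign.

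**The case against.** The strongest objection is scope. The sentence speaks of performance, while HbO2 is called a proxy for activation. The Background introduces dual-task cost with walking examples and gives percentages only for gait. A gait-only reading is possible. It is nowhere stated, though, and both the preceding sentence and Aim 3 point the other way. If gait only was meant, the same one-sentence change settles it.

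Second, the plan gives no denominator. Dividing by |ST| would remove the sign reversal. It would not cure the instability: at r = 1 the mean percentage over 50 participants still has a 95% range of about −91% to +827%.

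Third, sign disagreement at group level depends on how the percentage is summarised. This stands. A percentage computed from the two group means is almost never negative unless r is very low, and the median is much safer than the mean. The plan does not choose among these, and individual percentages remain affected whichever is used.

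Fourth, every size input is assumed, so the documents cannot show whether the problem is large or negligible here. This stands too.

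Fifth, the HbO2 outcome is defined for the walking conditions, so the standing case may never arise. It is an added risk only.

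Finally, the harm is limited. A sound absolute measure is already planned, and no test or sample size rests on the percentage.

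**Conclusion.** The concern holds and should be fixed. That the percentage is undefined at zero and depends on the standing reference follows from how HbO2 is defined. The sign reversal follows from the usual signed denominator. Application to HbO2 is the natural reading and not an explicit statement, so confidence is medium.

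The practical size depends on a single-task mean/SD ratio that the protocol does not give. At a ratio of 1, about 8 of 50 participants per subgroup would have a reversed sign; at 3, almost none. These shares assume normality. The group-level figures also assume the size and spread of the dual-task change. The damage is confined to whatever is reported or compared as an HbO2 percentage.

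**What to change.** Amend the dual-task interference sentence in the part 1 section on data management and analysis. Suggested wording: *Relative (percentage) change will be calculated only for positive ratio-scale measures, such as velocity, cadence, step time and cognitive scores of that kind. For HbO2, dual-task interference is the absolute change from single-task to dual-task in concentration units.* If a unit-free HbO2 figure is wanted, add a standardised mean difference.

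This needs no new data and changes no test procedure. The only loss is a percentage figure for HbO2.
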